11.7.1 Adverse Event of Special Interest

The following AEs will be considered and monitored as AEs of special interest (AESIs): musculoskeletal disorders, CPK increases, and rhabdomyolysis; hypersensitivity reactions, cardiac events and transaminase elevations, thromboembolic events, and hepatobiliary disorders.

If at any time AST/ALT levels are greater than 3 x ULN (> 5 x ULN if pre-existent liver involvement at baseline by the underlying disease, with baseline ALT levels between 3-5 x ULN):

- Report as an AESI.
- The investigator should ensure that serum liver enzyme tests, serum bilirubin, and coagulation tests (INR or equivalent) are repeated two or three times weekly (local labs). Frequency of re-

testing can decrease to once a week or less if abnormalities stabilise or the trial drug has been discontinued and the subject is asymptomatic.

- The list of concomitant medications should be re-checked, and include nonprescription drugs, herbal and supplementary preparations, alcohol and recreational substances.
- Other reasons for liver injury should be ruled out, including co-infection with other virus, autoimmune or alcoholic hepatitis, non-alcoholic liver steato-hepatitis, biliary tract disease, progression of an underlying disease (e.g. liver metastasis), hypoxic/ischemic hepatopathy, or exposure to environmental agents.
- The investigator should consider additional tests to evaluate liver function or structure, as well as a consultation to specialists in liver diseases.

Treatment with plitidepsin must be discontinued in case of:

- ALT or AST > 8 x ULN;
- ALT or AST > 3 x ULN and either total bilirubin >2 x ULN or INR >1.5;
- ALT or AST > 3xULN with the appearance of fatigue, nausea, vomiting, right upper quadrant pain or tenderness, fever, rash, and/or eosinophilia (>5%).

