7.2.1 Adverse Event of Special Interest

The following AEs will be considered and monitored as AEs of special interest (AESIs): musculoskeletal disorders, CPK increases, and rhabdomyolysis; hypersensitivity reactions, cardiac events and transaminase elevations, thromboembolic events, hepatobiliary disorders, and healthcare-associated infections (87).

If at any time AST/ALT levels are greater than 3 x ULN ($> 5 \times \text{ULN}$ if pre-existent liver involvement at baseline by the underlying disease, with baseline ALT levels between 3-5 x ULN):

- Report as an AESI.
- The investigator should ensure that serum liver enzyme tests, serum bilirubin, and coagulation tests (INR or equivalent) are repeated two or three times weekly (local labs). Frequency of re-testing can decrease to once a week or less if abnormalities stabilise or the trial drug has been discontinued and the subject is asymptomatic.
- The list of concomitant medications should be re-checked, and include nonprescription drugs, herbal and supplementary preparations, alcohol and recreational substances.
- Other reasons for liver injury should be ruled out, including co-infection with other virus, autoimmune or alcoholic hepatitis, non-alcoholic liver steato-hepatitis, biliary tract disease, progression of an underlying disease (e.g. liver metastasis), hypoxic/ischemic hepatopathy, or exposure to environmental agents.
- The investigator should consider additional tests to evaluate liver function or structure, as well as a consultation to specialists in liver diseases.

Treatment with pitidepsin must be discontinued in case of:

- ALT or AST $> 8 \times \text{ULN}$;
- ALT or AST $> 3 \times \text{ULN}$ and either total bilirubin $> 2 \times \text{ULN}$ or INR > 1.5 ;
- ALT or AST $> 3 \times \text{ULN}$ with the appearance of fatigue, nausea, vomiting, right upper quadrant pain or tenderness, fever, rash, and/or eosinophilia ($> 5\%$).

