2.0 Change History

Version/Date	Change Log
1.0	Created as new
2.0	Protocol has been updated to correct some errors detected and to implement some changes in response to clarifications requested by different drug agencies from the countries where the NEREIDA study is going to be carried out After IDMC Organizational meeting held on 22Feb23 some requests/clarifications have been also added. After agreement, Bayesian analyses will be performed by another CRO 'Phastar'.
3.0	Due to low recruitment, early study closure has been decided on 23Feb24. Therefore, SAP is abridged to provide the essential results for an abbreviated Clinical Study Report.

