6.0 Introduction

This SAP should be read in conjunction with the study protocol and case report form (CRF). Any further changes to the protocol or CRF may necessitate updates to the SAP. A first version of the SAP is expected prior to first patient in (FPI) and final approval of the SAP will occur prior to database lock. Due to low recruitment, early study closure was held on 23Feb24. Therefore, SAP is abridged to provide the essential results for an abbreviated Clinical Study Report (CSR) where information related to safety and descriptive efficacy results will be described. Study objectives, endpoints and populations will be adapted accordingly in order to present the most relevant data.

Consequently, no formal statistical significance tests will be presented, although the descriptive tables will allow a numerical comparison of the characteristics and outcomes of the patients in the experimental and control arm across the subgroups.

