8.3 Endpoints

Efficacy primary endpoint:

- 1-month† all-cause mortality rate. †(Day 30 since randomisation).

Key secondary endpoint:

- Time to confirmed negativisation in SARS-CoV-2 antigen test or RT-PCR Ct > 30.

Secondary endpoints:

Efficacy secondary endpoints

- Time to sustained end of COVID-related hospital care from the time of randomisation. Sustained discharge is defined as no subsequent admission within 30 days of initial end of hospital care [up to day 60 (± 3)], related to either COVID-19 or COVID-19 therapy.
- Time to sustained improvement (defined in Protocol Section 7.1.3) and resolution of selected COVID signs/symptoms (See Protocol Appendix 10 - COVID-19 signs/symptoms checklist).
- Distribution of patients according to their clinical status by the 11-category WHO Clinical Progression Scale, at Days 4 (± 1), 8 (± 1), 15 (± 1), 30 (± 2), and 60 (± 3) (See Protocol Appendix 1 – 11-Point World Health Organization (WHO) Clinical Progression Scale).
- Percentage of patients requiring oxygen therapy on Days 4 (± 1), 8 (± 1), 15 (± 1), 30 (± 2), and 60 (± 3).
- Time to sustained discontinuation (i.e., at least 7 days) of oxygen supplementation.

Safety secondary endpoints

Frequency of the following events (all-cause and drug-related):

- Treatment-emergent adverse events (TEAEs);
- TEAEs \geq grade 3 according to the National Cancer Institute [NCI]-Common Terminology Criteria for AEs (CTCAE v.5.0);
- Adverse events of special interest (AESIs);
- Serious adverse events (SAEs);
- Drug related Serious Adverse Events (i.e., SARs);
- Adverse events leading to treatment discontinuation; and
- Deaths (COVID-19-related/all).
- Change respect to baseline* in individual study-defined laboratory parameters (See Protocol Section 5.7, 5.8 and 5.9 and Protocol Appendix 8 – Clinical Laboratory Analyses).
- Change respect to baseline* in individual vital signs (See Protocol Section 5.7, 5.8 and 5.9).

*Baseline = latest test performed between screening and drug administration

Other Secondary/Exploratory Endpoints

- Percentage of patients requiring advanced oxygen support on Days 4 (± 1), 8 (± 1), 15 (± 1), 30 (± 2) and 60 (± 3).
- Time to intensification of respiratory support (WHO >5) (See Protocol Appendix 1 – 11-Point World Health Organization (WHO) Clinical Progression Scale).
- Total duration of advanced oxygen support.
- Percentage of patients requiring high-flow oxygen on Days 4 (± 1), 8 (± 1), 15 (± 1), 30 (± 2), and 60 (± 3).

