11.0 Statistical Methods

Non-continuous variables will be described in frequency tables using counts and percentages. Continuous variables will be described by median, mean, standard deviation (STD), interquartile range (Q1-Q3),

minimum and maximum. Study endpoints will be summarized by means of tables, listings for all CRF variables and figures for temporal series as viral load, lymphocytes/neutrophils evolution, LDH, CT>30 or oxygen necessities as well as Kaplan-Meier figures, as inverse KM (see section 11.8) where time to event data Y-axis started from 0% instead the usual 100%, e.g. time to confirmed negativisation in SARS-CoV-2 antigen test or RT-PCR Ct > 30, will be shown.

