11.7 Safety Analyses

Safety analyses will be based on the As Treated Population. All safety parameters will be summarised, plotted and also listed by patient/events.

A treatment-emergent adverse event is defined as any event not present prior to the initiation of the treatments or any event already present that worsens in intensity following exposure to the treatments.

Treatment-emergent Adverse Events: The verbatim terms used in the electronic case report form (eCRF) by investigators to identify TEAEs will be coded using the Medical Dictionary for Regulatory Activities (MedDRA) and will be graded according to NCI CTCAE version 5.0. Treatment-emergent AEs will be summarised by MedDRA system organ class and preferred term by number of patients and by number of events. For each TEAE, the percentage of subjects who experience at least 1 occurrence of the TEAE will be summarised overall and by treatment group. The SAEs, AEs of special interest, and deaths will be listed including the study period (see Section 8.2) that they occur. All TEAEs resulting in discontinuation of study treatment will be listed and summarised by system organ class/preferred term.

AEs, SAEs, deaths, laboratory evaluations, and study drug discontinuations due to AEs will be tabulated in a descriptive way. Counts and percentages will be used for categorical variables, and summary tables will be used for continuous variables.

Any treatment-related adverse events (including Unknown relationship but potentially related), treatment-emergent adverse events of special interest, and SAES (including those with seriousness missing) that will be measured daily until resolution or stabilisation to at least Grade 1, or to an acceptable level according to the investigator and the sponsor of his/her designated representative.

Clinical Laboratory Tests, see protocol sections 5.5.1/5.7/5.8/5.9 and appendix 8 to differentiate local or central. Laboratory data will be summarised by type of laboratory test. The worst toxicity grade will be tabulated. Parameters with predefined NCI CTCAE version 5.0 toxicity grades will be summarised. Change from baseline to the worst TEAE grade experienced by the subject during the study will be provided as shift tables.

- Haematology: haematocrit, red blood cells (RBC), differential WBC counts (including neutrophil and lymphocyte counts), platelet count and haemoglobin.

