11.8 Summary of Statistical Tests

All the main characteristics for estimands to fulfill study objectives will be defined as footnotes in each table following a similar structure than primary estimand definition. Below it can be found the endpoints to measure the variable definition and the analysis method to be used. Treatment attribute is maintained as 'participants will be randomised to receive plitidepsin versus control in each group' whereas applicable and sensitivity analyses according populations defined in 8.5 will be calculated. For intercurrent events, while applicable, a treatment-policy strategy as defined for the primary estimand will be followed.

Table 3 Summary of statistical tests

Endpoints	Analyses	Population
Efficacy primary endpoint		
1-month all-cause mortality rate.	-Frequencies	-FAS population
Key secondary endpoint		
Time to confirmed negativisation in SARS-CoV-2 antigen test or RT-PCR Ct > 30.	-Kaplan-Meier (unstratified)	-FAS population

Endpoints	Analyses	Population
Efficacy secondary endpoints		
Time to sustained end of COVID-related hospital care from the time of randomisation. Sustained discharge is defined as no subsequent admission within 30 days of initial end of hospital care [up to day 60 (± 3)], related to either COVID-19 or COVID-19 therapy	-Kaplan-Meier (unstratified)	-FAS population
Time to sustained improvement (defined in Protocol Section 7.1.3) and resolution of selected COVID signs/symptoms (See Protocol Appendix 10 - COVID-19 signs/symptoms checklist).	-Kaplan-Meier (unstratified)	-FAS population
Distribution of patients according to their clinical status by the 11-category WHO Clinical Progression Scale, at Days 4 (± 1), 8 (± 1), 15 (± 1), 30 (± 2), and 60 (± 3) (See Protocol Appendix 1 – 11-Point World Health Organization (WHO) Clinical Progression Scale).	-Frequencies	-FAS population
Percentage of patients requiring oxygen therapy on Days 4 (± 1), 8 (± 1), 15 (± 1), 30 (± 2), and 60 (± 3).	-Frequencies	-FAS population
Time to sustained discontinuation (i.e., at least 7 days) of oxygen supplementation.	-Kaplan-Meier (unstratified)	-FAS population
Safety secondary endpoints		
Treatment-emergent adverse events (TEAEs).	-Frequencies (severity grade by NCI-CTCAE v5)	-As treated population
TEAEs \geq grade 3 according to the National Cancer Institute	-Frequencies	-As treated population

Endpoints	Analyses	Population
[NCI]-Common Terminology Criteria for AEs (CTCAE v.5.0).		

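### The SAP's list of adverse events of special interest drops healthcare-associated infections, which the protocol includes, without a stated reason

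*SAP*

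**What the plan says.** Protocol 7.2.1 defines the AESIs in one sentence that closes with "thromboembolic events, hepatobiliary disorders, and healthcare-associated infections". It cites a published surveillance definition for the last of these. Protocol 3.3.2 makes AESI frequency, all-cause and drug-related, a safety secondary endpoint.

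SAP 11.7.1 opens with the same sentence and keeps the earlier terms in the same order, but its list ends with "hypersensitivity reactions, cardiac events and transaminase elevations, thromboembolic events, and hepatobiliary disorders". The liver-test text that follows is carried over from the protocol. Healthcare-associated infections appear nowhere in the SAP.

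The abridged SAP still plans to report AESIs in three places:
- SAP 8.3 keeps them among the safety secondary endpoints.
- SAP 11.7 plans a listing: "The SAEs, AEs of special interest, and deaths will be listed including the study period".
- SAP 11.8, Table 3, plans frequencies by severity grade in the As Treated population.

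On the reason for changes, the entry for version 3.0 in SAP 2.0 says that, after early closure for low recruitment, the "SAP is abridged to provide the essential results for an abbreviated Clinical Study Report". SAP 6.0 adds that objectives, endpoints and populations will be adapted. Neither mentions the AESI definition.

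**The concern.** The two documents define the same safety endpoint differently, and nothing in the SAP marks the difference as deliberate. The SAP list is worded as complete: it is not introduced as a set of examples and does not refer back to Protocol 7.2.1. A programmer working from it would produce an AESI table and listing without the infection category, and a reader of the report would have no sign that a protocol-defined category had been left out.

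The omitted category matters in this trial. Every patient is immunocompromised. Protocol 1.2.1.3.2 takes infection incidence as its first line of evidence on whether plitidepsin is immunosuppressive, in both the cancer and the COVID-19 data. The study rationale (Protocol 1.3) relies on there being no such signal.

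**Working it through.** No sample size, power or error rate is involved. The check compares the two lists and then searches for a reason and for substitute outputs.

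**Step 1: the lists side by side.**

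| Term | Protocol 7.2.1 | SAP 11.7.1 |
|---|---|---|
| Musculoskeletal disorders | yes | yes |
| CPK increases | yes | yes |
| Rhabdomyolysis | yes | yes |
| Hypersensitivity reactions | yes | yes |
| Cardiac events | yes | yes |
| Transaminase elevations | yes | yes |
| Thromboembolic events | yes | yes |
| Hepatobiliary disorders | yes | yes |
| Healthcare-associated infections | yes | **no** |

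Counting every term, the protocol has 9 and the SAP has 9 − 1 = 8. Treating the three muscle terms as one category removes 2 from each count, giving 7 and 6. Treating cardiac events and transaminase elevations as one category as well removes 1 more, giving 6 and 5. The difference is one category on any count.

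**Step 2: is a reason given?** The change history and introduction give only a general reason for abridging. Elsewhere the SAP usually says explicitly what it drops because of early closure:
- two comparative or predictive objectives (7.3)
- per-protocol and sensitivity outputs (8.6.2.2)
- Bayesian and other complex outputs (11.6, 11.6.1, 11.6.2 and the note after Table 3)
- reports for the data monitoring committee (11.7.2)
- subgroup outputs (11.10)

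Section 11.7.1 carries no such statement. Since the AESI endpoint, listing and table were all kept, general abridgement does not explain the loss of one category.

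**Step 3: which list governs the outputs?** SAP 6.0 says the SAP is to be read together with the protocol and the case report form, but sets no order of precedence between them. The documents do not say whether AESIs are flagged by investigators in the eCRF, under Protocol 7.2.1, or derived at analysis from the SAP list. The effect on the outputs is therefore conditional.

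**Step 4: where would the infections still be seen?**
- Treatment-emergent adverse events are tabulated by system organ class, preferred term and grade in the As Treated population (SAP 11.7 and 11.8).
- Serious cases appear in the SAE table and listing.
- SAP 11.0 promises "listings for all CRF variables".
- SAP 8.3 and 11.8 keep the percentage of patients with a new infection by Days 4, 8, 15, 30 and 60.

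The new-infection endpoint is the nearest substitute, but it is not equivalent. It covers any new infection, has no grading specified and uses the Full Analysis Set. By SAP 8.6.2.1 that set requires randomisation, at least one dose, and either survival follow-up to Day 30 or death. The As Treated population takes everyone exposed, including any treated patients in the non-randomised Group 4.

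**The case against.** The best case against is that no effect on outputs has been shown. SAP 11.7.1 is mostly the protocol's monitoring text copied across, with instructions to investigators. It contains no coding query, term list or flag from which AESIs would be derived. Sites monitor under the protocol, and the SAP is to be read with it, so the outputs may well follow what sites reported under Protocol 7.2.1. If the eCRF carries an AESI flag, the listings of CRF variables would show it. SAP 6.0 does announce that endpoints will be adapted. The retained new-infection endpoint, under a retained superinfection objective, also means that infection frequency by arm is reported anyway.

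Much of this stands as a limit on importance. A narrower AESI table is possible, not demonstrated, and the infections themselves are not lost. It is also fair to say that the SAP gives no *specific* reason, as opposed to no reason of any kind. None of it removes the mismatch: the lists differ, the endpoint is kept, no rule says which list prevails, and the new-infection output differs in population and definition and has no grading specified.

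**Conclusion.** The concern holds, as a minor inconsistency between protocol and SAP. It is certain that SAP 11.7.1 omits one category that Protocol 7.2.1 includes, and that the SAP does not explain the omission.

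The consequence depends on one assumption: that the AESI outputs are built from the SAP list. If so, a protocol-defined safety secondary endpoint is reported on a narrower definition, without healthcare-associated infections. If AESIs are instead taken from an eCRF flag set under the protocol, only the SAP text is wrong.

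The number of events at stake cannot be estimated, because the documents give no rate of healthcare-associated infection. Reporting is descriptive, no formal test uses the result, and the SAP attaches no decision rule to AESI frequency.

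**What to change.** Restore healthcare-associated infections to the list in SAP 11.7.1, so that the AESI listing and table match Protocol 7.2.1. If the category was removed on purpose, enter the removal and its reason in the SAP change history, and state the difference from Protocol 7.2.1 in the abbreviated clinical study report.

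The first option costs one phrase. The second costs one line in each document. If AESIs are already flagged in the eCRF under the protocol, restoring the phrase changes no output. SAP 6.0 places final SAP approval before database lock; if lock has passed, disclosure in the report is still possible.
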